**Original Release: 16-Nov-2016****Current Version: 29-Apr-2020****Revision History**

Revision Number	Release Date	Template Version	Reason for Change
A	16-Nov-2016	90702637 Rev/Ver AG	Not Applicable
B	15-Feb-2017	90702637 Rev/Ver AG	See Table 26.1-1
C	23-Sep-2018	90702637 Rev/Ver AG	
D	21-Nov-2018	90702637 Rev/Ver AG	
E	25-Feb-2020	90702637 Rev/Ver AG	
F	29-Apr-2020	90702637 Rev/Ver AL	

## 2. Protocol Synopsis

[figure not shown]
REPRISE IV: REpositionable Percutaneous Replacement of Stenotic Aortic Valve through Implantation of LOTUS Edge™ Valve System in Intermediate Surgical Risk Subjects					
Study Objective(s)	To evaluate safety and effectiveness of the LOTUS Edge ™ Valve System when used with the Lotus ™ or iSleeve ™ Introducer Sets for transcatheter aortic valve replacement (TAVR) in symptomatic subjects with severe aortic stenosis who are considered at intermediate risk for surgical valve replacement including those who have a bicuspid native valve.				
Intended Use	
The LOTUS Edge Valve System is intended to improve aortic valve function in symptomatic subjects with severe aortic stenosis who are at intermediate risk for standard surgical aortic valve replacement (SAVR), including those who have a bicuspid native valve.
 
The iSleeve and Lotus Introducer Sets are intended to provide percutaneous access to the vascular system.
				
Test Device(s) and Sizes	
REPRISE IV uses the following investigational device.
 
  
 Device Name/Size	Description	
   
            LOTUS Edge Valve System            Valve diameter:            - 23mm            - 25mm            - 27mm         	           Includes 2 main components:            - a bioprosthetic bovine pericardial aortic valve (similar to the Lotus™ Valve System used in the REPRISE III IDE study [NCT02202434] and the RESPOND post-market surveillance study [NCT02031302])            - a next generation delivery system designed to increase flexibility, trackability, and coaxial alignment            The LOTUS Edge Valve System is introduced percutaneously via the femoral artery.         	
  
 
The iSleeve™ Introducer Set (iSleeve) and the large Lotus Introducer Set (LIS-L) can be used as accessories to facilitate vascular introduction and deployment of the LOTUS Edge Valve System (23mm, 25mm, and 27mm valve sizes). The iSleeve has an expandable sheath component and a dilator enabling access to transfemoral arteries <math>\geq 5.9</math> mm. The LIS-L is intended for use in subjects with femoral vascular access <math>\geq 6.5</math> mm. In countries where the introducer sets are approved, the commercial devices
	Device Name/Size	Description	LOTUS Edge Valve System Valve diameter: - 23mm - 25mm - 27mm	Includes 2 main components: - a bioprosthetic bovine pericardial aortic valve (similar to the Lotus ™ Valve System used in the REPRISE III IDE study [NCT02202434] and the RESPOND post-market surveillance study [NCT02031302]) - a next generation delivery system designed to increase flexibility, trackability, and coaxial alignment The LOTUS Edge Valve System is introduced percutaneously via the femoral artery.
Device Name/Size	Description				
LOTUS Edge Valve System Valve diameter: - 23mm - 25mm - 27mm	Includes 2 main components: - a bioprosthetic bovine pericardial aortic valve (similar to the Lotus ™ Valve System used in the REPRISE III IDE study [NCT02202434] and the RESPOND post-market surveillance study [NCT02031302]) - a next generation delivery system designed to increase flexibility, trackability, and coaxial alignment The LOTUS Edge Valve System is introduced percutaneously via the femoral artery.				

REPRISE IV: REpositionable Percutaneous Replacement of Stenotic Aortic Valve through Implantation of LOTUS Edge™ Valve System in Intermediate Surgical Risk Subjects	
	will be used. In countries where they are not approved, they will be considered investigational devices.
Comparator	For the primary endpoint, a performance goal (PG) based on 1-year TAVR outcomes derived from published literature will be used as the comparator for analysis.
Study Design	
REPRISE IV is a prospective, multicenter single-arm study designed to evaluate the safety and effectiveness of the LOTUS Edge Valve System for TAVR in symptomatic subjects who have severe native aortic stenosis and are considered at intermediate risk for surgical valve replacement. Study cohorts include the following.
 
 
• Main Cohort: A prospective, multicenter, single-arm cohort of subjects with severe aortic stenosis who are considered at intermediate risk for surgical aortic valve replacement and are treated with the LOTUS Edge Valve System. 
 
○ CT Imaging Substudy: Selected centers with the ability to perform high quality 4D computed tomography (CT) scans will include subjects from the Main Cohort in a CT imaging substudy to assess the prevalence of reduced leaflet mobility and its relationship, if any, to clinical events.
 
 
 
• Bicuspid Nested Registry: A prospective, single-arm, nested registry cohort of subjects who have a native bicuspid aortic valve, are considered at intermediate risk for surgical aortic valve replacement and are treated with the LOTUS Edge Valve System.
 
• Roll-In Cohort: A roll-in phase with the study device for centers that do not have implantation experience with the LOTUS Edge Valve System; each of these centers will perform at least 2 roll-in cases before commencing enrollment in the evaluable Main Cohort and Bicuspid Nested Registry. Data from roll-in subjects will be summarized separately from the evaluable Main Cohort and Bicuspid Nested Registry. Roll-in subjects will not be included in the primary endpoint analysis.
 
 
The REPRISE IV study will be conducted in accordance with 21 CFR Parts 11, 50, and 54; the relevant parts of the International Conference on Harmonisation (ICH) Guidelines for Good Clinical Practices (GCP); the International Standard ISO 14155 Clinical Investigation of Medical

**REPRIS E IV: REpositionable Percutaneous Replacement of Stenotic Aortic Valve through Implantation of LOTUS Edge™ Valve System in Intermediate Surgical Risk Subjects**

Devices for Human Subjects – Good Clinical Practice; ethical principles that have their origins in the Declaration of Helsinki; and pertinent individual country/state/local laws and regulations. The study shall not begin until the required approval/favorable opinion from the Institutional Review Board/Human Research Ethics Committee (IRB/HREC) and/or regulatory authority has been obtained, if appropriate.

The study design is summarized in the figure below.

\* Subjects are considered enrolled when an attempt is made to insert the LOTUS Edge Transfemoral Aortic Valve System into the femoral artery.  
 † Discharge or 7 days, whichever comes first  
 ‡ Includes clinic/in-person visit at 30 days and years 1–5, 7 & 10; telephone follow-up at years 6, 8 & 9. Enrolled subjects who do not have a study device implanted will be assessed through 1 year post procedure for safety.

**REPRIS E IV Study Design Overview**

**Planned Number of Subjects/ Investigational Centers/ Countries**

Subjects will be enrolled at up to 65 centers in the United States and Australia. There will be up to 926 subjects enrolled in REPRIS E IV as shown below.

Cohort	Number of Subjects
Main	696*
Bicuspid Nested Registry	100
Roll-In	Up to 130

\* Up to 200 subjects from the main cohort will be enrolled in the CT Imaging Substudy. If 200 subjects have not enrolled in the CT Imaging Substudy by completion of enrollment in the main cohort, additional subjects who meet the REPRIS E IV eligibility criteria will be enrolled in a separate CT Imaging Cohort to achieve a total of 200 subjects in the CT Imaging Substudy.

REPRISE IV: REpositionable Percutaneous Replacement of Stenotic Aortic Valve through Implantation of LOTUS Edge™ Valve System in Intermediate Surgical Risk Subjects	
Primary Endpoint	Composite of all-cause mortality and all stroke at 1 year.
Additional Measurements	
Additional measurements based on the VARCa endpoints and definitions will be collected peri- and post-procedure, at discharge or 7 days post-procedure (whichever comes first), 30 days, and annually through 10 years post index procedure, unless otherwise specified below.
 
 
• Safety endpoints adjudicated by an independent Clinical Events Committee (CEC): 
 
○ Mortality: all-cause, cardiovascular, and non-cardiovascular
 
○ Stroke: disabling and non-disabling
 
○ Myocardial infarction (MI): periprocedural (<math>\leq 72</math> hours post index procedure) and spontaneous (<math>> 72</math> hours post index procedure)
 
○ Bleeding: life-threatening (or disabling) and major (through 5 years)
 
○ Acute kidney injury (<math>\leq 7</math> days post index procedure): based on the AKIN System Stage 3 (including renal replacement therapy) or Stage 2
 
○ Major vascular complication (through 5 years)
 
○ Repeat procedure for valve-related dysfunction (surgical or interventional therapy)
 
○ Hospitalization for valve-related symptoms or worsening congestive heart failure (NYHA class III or IV)
 
○ New permanent pacemaker implantation resulting from new or worsened conduction disturbances
 
○ New onset of atrial fibrillation or atrial flutter
 
○ Coronary obstruction: periprocedural (<math>\leq 72</math> hours post index procedure)
 
○ Ventricular septal perforation: periprocedural (<math>\leq 72</math> hours post index procedure)
 
○ Mitral apparatus damage: periprocedural (<math>\leq 72</math> hours post index procedure)
 
○ Cardiac tamponade: periprocedural (<math>\leq 72</math> hours post index procedure)
 
 
 

**REPRISE IV: REpositionable Percutaneous Replacement of Stenotic Aortic Valve through Implantation of LOTUS *Edge*™ Valve System in Intermediate Surgical Risk Subjects**

- Prosthetic aortic valve malpositioning, including valve migration, valve embolization, or ectopic valve deployment
- Transcatheter aortic valve (TAV)-in-TAV deployment
- Prosthetic aortic valve thrombosis
- Prosthetic aortic valve endocarditis
- Device Performance endpoints peri- and post-procedure:
  - Successful vascular access, delivery and deployment of the study valve, and successful retrieval of the delivery system
  - Successful retrieval of the study valve if retrieval is attempted
  - Successful repositioning of the study valve if repositioning is attempted (see **Note 1** below)
  - Grade of aortic valve regurgitation: paravalvular, central, and combined
- Device success, defined as absence of procedural mortality, correct positioning of a single valve into the proper anatomical location, intended performance of the study device (effective orifice area [EOA]  $>0.9 \text{ cm}^2$  for  $\text{BSA} <1.6 \text{ m}^2$  and  $\text{EOA} >1.1 \text{ cm}^2$  for  $\text{BSA} \geq 1.6 \text{ m}^2$  plus either a mean aortic valve gradient  $<20 \text{ mm Hg}$  or a peak velocity  $<3 \text{ m/sec}$ , and no moderate or severe prosthetic valve aortic regurgitation)
- Additional indications of prosthetic aortic valve performance as measured by transthoracic echocardiography (TTE; see **Note 2** and **Note 3** below) and assessed by an independent core laboratory, including effective orifice area, mean and peak aortic gradients, peak aortic velocity, and grade of aortic regurgitation
- Functional status as evaluated by the following:
  - 5-m gait speed test (at 1 year compared to baseline)
  - New York Heart Association (NYHA) classification (see **Note 3** below)
- Neurological status as determined by the following:
  - National Institutes of Health Stroke Scale (NIHSS) and modified Rankin Scale (mRS) assessments, which must be performed at baseline and pre-specified timepoints for all enrolled subjects (see **Note 4** below). NIHSS and mRS must be performed by a neurology professional or certified personnel.

REPRIS E IV: REpositionable Percutaneous Replacement of Stenotic Aortic Valve through Implantation of LOTUS Edge™ Valve System in Intermediate Surgical Risk Subjects	
	
 
○ For subjects diagnosed with a stroke, a neurological physical exam, mRS, and NIHSS must be performed after the event; mRS must also be administered at 90±14 days following a stroke; the simplified mRS questionnaire may be used for this follow-up assessment. The neurological physical exam must be conducted by a neurologist, neurology fellow, neurology physician assistant, or neurology nurse practitioner.
 
● Health status as evaluated by Kansas City Cardiomyopathy and SF-12 Quality of Life questionnaires at baseline, 1 month, and 1 and 5 years.
 
● For subjects in the Bicuspid Nested Registry, a CT scan at 30 days post LOTUS Edge Valve implantation. The data will be evaluated by an independent CT core laboratory.
 
● For subjects in the CT Imaging Substudy, a 4D CT scan at 30 days and at 1 year post LOTUS Edge valve implantation to assess the prevalence of reduced leaflet mobility and its relationship, if any, to clinical events. The data will be evaluated by an independent CT core laboratory.
 
 
Note 1: For the LOTUS Edge valve, repositioning may be achieved with partial or full resheathing of the valve.
 
Note 2: At least 1 echocardiogram must be obtained before discharge or 7 days (whichever comes first); if multiple echocardiographic studies are performed prior to discharge and within 7 days of the procedure, the latest study performed will be used for analysis.
 
Note 3: Echocardiography and NYHA assessment are not required in years 6, 8, and 9 (telephone follow-up only).
 
Note 4: NIHSS is required at discharge and 1 year; mRS is required at all follow-up visits up to 5 years.
 
a: Leon M, et al. J Am Coll Cardiol. 2011;57:253–69              Kappetein AP, et al. J Am Coll Cardiol. 2012;60:1438–54

Method of Assigning Subjects to Treatment	
Main Cohort: Subjects with severe aortic valve stenosis who meet all eligibility criteria may be treated with the LOTUS Edge Valve System.
 
 
- Up to 200 subjects from the main cohort will be enrolled in the CT Imaging Substudy. If 200 subjects have not enrolled in the CT Imaging Substudy by completion of enrollment in the main cohort, additional subjects who meet the REPRIS E IV eligibility criteria
 

REPRISE IV: REpositionable Percutaneous Replacement of Stenotic Aortic Valve through Implantation of LOTUS Edge™ Valve System in Intermediate Surgical Risk Subjects	
	
will be enrolled in a separate CT Imaging Cohort to achieve a total of 200 subjects in the CT Imaging Substudy.
 
Bicuspid Nested Registry: Subjects with a native bicuspid aortic valve who meet all inclusion criteria and have no other exclusion criterion may be treated with the LOTUS Edge Valve System as part of a single-arm, nested registry cohort.
 
Roll-In Cohort: For centers that do not have implantation experience with the LOTUS Edge Valve System 2 to 4 roll-in subjects will be treated before commencing enrollment in the Main Cohort and Bicuspid Nested Registry.

Follow-up Schedule	
All subjects implanted with a study device will be assessed at baseline, peri- and post-procedure, at discharge or 7 days post-procedure (whichever comes first), 30 days, 1 year, and then annually for up to 10 years post-procedure. Subjects who are enrolled but not implanted with a study device at the time of the procedure will be followed for safety through 1 year.
 
The visits at 30 days, 1–5 years, 7 years, and 10 years are to be an office/clinical or in-person visit but may be done in-hospital should the subject be admitted at the time. Telephone follow-up is allowed at 6, 8, and 9 years. Procedures at each scheduled visit are described above under “Additional Measurements.”

Study Duration	
Subjects implanted with a study device will be followed for 10 years after the index procedure.
 
Enrollment is expected to be completed in approximately 24 months; therefore, the total study duration is estimated to be approximately 12 years.

Participant Duration	
The study duration for each subject is expected to be approximately 10 years.

Adjunctive Pharmacologic Therapy	
Anticoagulant Therapy
 
Anticoagulant therapy (e.g., unfractionated heparin) per local standard of care must be administered during the implant procedure, with a recommended target activated clotting time of <math>\geq 250</math> seconds during the index procedure.

**REPRISE IV: REpositionable Percutaneous Replacement of Stenotic Aortic Valve through Implantation of LOTUS *Edge*™ Valve System in Intermediate Surgical Risk Subjects**

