## 7. Study Design

### 7.1. Scale and Duration

The REPRISE IV clinical study includes a prospective, multicenter, single-arm trial (Main Cohort; N=696) designed to evaluate the safety and effectiveness of the LOTUS *Edge* Valve System when used with the Lotus™ Introducer Set or, when available, the iSleeve™ Introducer Set for TAVR in symptomatic subjects who have severe aortic stenosis and who are at intermediate risk for SAVR. There will be a roll-in phase (up to 130 subjects) for centers that do not have previous experience implanting the LOTUS *Edge* Valve. There will also be a single-arm nested registry cohort of subjects who have a bicuspid native valve to assess safety and effectiveness (Bicuspid Nested Registry; N=100). Selected centers with the ability to perform high quality 4D computed tomography (CT) scans will include up to 200 subjects from the Main Cohort in a CT Imaging Substudy to assess the prevalence of reduced leaflet mobility and its relationship, if any, to clinical events. All subjects in these

centers will be approached for consent to participate in the CT study. If 200 subjects have not enrolled in the CT Imaging Substudy by completion of enrollment in the main cohort, additional subjects who meet the REPRISE IV eligibility criteria will be enrolled in a separate CT Imaging Cohort to achieve a total of 200 subjects in the CT Imaging Substudy. **Figure 7.1-1** shows the study design.

\* Up to 200 subjects from the main cohort will be enrolled in the CT Imaging Substudy. If 200 subjects have not enrolled in the CT Imaging Substudy by completion of enrollment in the main cohort, additional subjects who meet the REPRISE IV eligibility criteria will be enrolled in a separate CT Imaging Cohort to achieve a total of 200 subjects in the CT Imaging Substudy.

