## 7.3. *Justification for the Study Design*

There will be up to 926 subjects in REPRISE IV. In order to support the stated objectives of this study (see Section **6.1**) while also limiting the potential exposure of study subjects to risk, up to 130 subjects will be enrolled in the roll-in phase of this study (at centers without previous LOTUS *Edge* valve experience), 696 subjects will be enrolled in the Main Cohort, and 100 subjects will be enrolled in the Bicuspid Nested Registry cohort. Up to 65 centers in the United States and Australia will participate in the study. Safety and effectiveness results will be reported on all enrolled subjects (see Section **19** for information on safety reporting). In addition to the risk-benefit analysis noted in Section **4.2** (see also Section **18**), ongoing dynamic data safety monitoring will be performed throughout the trial to minimize risk to subjects (see Section **21.1**). All implanted subjects will be followed for up to 10 years post index procedure. Per society guidelines antiplatelet therapy with aspirin and/or a P2Y12 inhibitor is recommended after TAVR to decrease the risk of thrombotic or thromboembolic complications if there are no contraindications to these medications.

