#### 11.1.2. **Baseline Comparability**

Baseline data will be summarized separately for subjects in the Main Cohort, Roll-In Cohort, and Bicuspid Nested Registry Cohort. Subject demographics, clinical and neurological history, risk factors, and pre-procedure characteristics will be summarized using descriptive statistics (e.g., mean, standard deviation, n, minimum, maximum) for continuous variables and frequency tables or proportions for discrete variables. Procedural characteristics will be summarized similarly.

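### The stated maximum of 926 subjects leaves out the conditional CT Imaging Cohort, which could take enrollment as high as 1,126

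*Combined protocol and SAP*

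**What the plan says.** The Synopsis row on planned numbers states: "There will be up to 926 subjects enrolled". The table beneath it has three rows: Main 696, Bicuspid Nested Registry 100 and Roll-In up to 130. An asterisk on the 696 leads to a footnote: "Up to 200 subjects from the main cohort will be enrolled in the CT Imaging Substudy". The footnote then covers a shortfall. "If 200 subjects have not enrolled in the CT Imaging Substudy by completion of enrollment in the main cohort", additional eligible subjects "will be enrolled in a separate CT Imaging Cohort to achieve a total of 200 subjects in the CT Imaging Substudy". The Synopsis row on assigning subjects to treatment and Section 7.1 give the same rule.

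Section 7.3 restates the total as "There will be up to 926 subjects in REPRISE IV" and itemizes it: "up to 130 subjects will be enrolled in the roll-in phase of this study", and "696 subjects will be enrolled in the Main Cohort, and 100 subjects will be enrolled in the Bicuspid Nested Registry cohort". It has no footnote and does not mention the CT Imaging Cohort. The itemized numbers are introduced as a balance between meeting the objectives and limiting subjects' exposure to risk.

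Section 11.1.2 says: "Baseline data will be summarized separately for subjects in the Main Cohort, Roll-In Cohort, and Bicuspid Nested Registry Cohort". Section 11.1.4 provides for summarizing the substudy's 4D CT data and exploring any link with clinical events.

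**The concern.** A figure given as a maximum should hold under every enrollment path that the protocol permits, and this one does not. The three listed cohorts use up the 926 with nothing to spare. The CT Imaging Cohort is called separate and opens only once the Main Cohort is full, so its subjects cannot be among the 696. They would be newly implanted patients: Section 6.2.2 times the substudy scans from implantation of the study valve.

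What is at stake is the accuracy of the enrollment and exposure ceiling that sites, ethics committees and regulators read. Section 7.3 is where that ceiling is justified on risk grounds, and a reader of that section alone would not learn that more subjects can be enrolled. The sponsor treats the number as one to keep current: the revision history shows it rising from 896 to 926 when the Roll-In maximum went from 100 to 130.

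A smaller, related gap is that the list of cohorts for baseline summaries in Section 11.1.2 does not include this one.

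**Working it through.** **Inputs**

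- Main Cohort: 696 (Synopsis table; Sections 7.1 and 7.3)
- Bicuspid Nested Registry: 100 (same places)
- Roll-In: up to 130 (same places)
- CT Imaging Substudy target: 200 (Synopsis footnote; Section 7.1)
- m, the number of Main Cohort subjects in the substudy: not given, so treated as an assumption between 0 and 200

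**Step 1: reproduce the stated total.** 696 + 100 + 130 = 926. This matches exactly and leaves no allowance for a fourth cohort.

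**Step 2: size of the separate cohort.** It is filled until the substudy reaches 200, so it holds 200 − m subjects.

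**Step 3: maximum under the protocol's own rules.** Maximum = 926 + (200 − m).

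| m (assumed) | Separate cohort | Maximum | Excess over 926 |
|---|---|---|---|
| 200 | 0 | 926 | 0% |
| 199 | 1 | 927 | 0.1% |
| 150 | 50 | 976 | 5.4% |
| 100 | 100 | 1,026 | 10.8% |
| 50 | 150 | 1,076 | 16.2% |
| 0 | 200 | 1,126 | 21.6% |

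**Step 4: when actual enrollment would pass 926.** With r Roll-In subjects (r at most 130) and the other two cohorts full, enrollment is 696 + 100 + r + (200 − m). This exceeds 926 when 200 − m is larger than 130 − r. A Roll-In phase that stops short can therefore absorb some or all of a substudy shortfall. This affects the number finally enrolled. It does not affect the maximum, which is taken at r = 130.

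**Step 5: does it touch the powered analysis?** Section 11.1.1.2 gives an expected rate p1 = 0.111, a performance goal p0 = 0.152, one-sided alpha 0.025 and power 87.5%. For a one-sample z-test with the null variance at the goal:

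n = [(z0.975 × √(p0(1 − p0)) + z0.875 × √(p1(1 − p1))) / (p0 − p1)]²

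This gives n = 674.8, against 675 stated. Power at n = 675 is 87.5%, as stated. Allowing for 3% attrition, 675 / 0.97 = 695.9, which rounds up to 696. The Main Cohort size therefore stands on its own. Sections 11.1.1.1 and 11.1.1.3 frame the hypothesis and the success criterion for the Main Cohort, so subjects in a separate cohort do not enter the test.

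**The case against.** The strongest reply is that nothing is hidden and no sum is wrong. The 926 is introduced as the total of the table below it, the three rows add up correctly, and the footnote on the 696 discloses the contingent cohort. The Synopsis repeats the contingency and so does Section 7.1. The cohort may never open: Section 7.1 says that all subjects at the selected CT centers will be asked to take part, and if 200 Main Cohort subjects join, 926 holds. All of this is fair, and it rules out calling 926 an arithmetic error.

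It does not rescue 926 as a maximum. The footnote explains where substudy subjects come from, but it never says that the total excludes those in the separate cohort. Section 7.3 gives the total with no footnote at all. A shortfall is also foreseeable. Only selected centers take part, consent is needed, and the substudy has three additional exclusion criteria (renal function, uncontrolled atrial fibrillation rate, expected chronic anticoagulation).

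A reader might go further and infer that the separate cohort has no place in any analysis. The documents do not support that. Its subjects are enrolled to complete the substudy, so the CT analysis in Section 11.1.4 covers them. Section 7.3 promises safety and effectiveness results on all enrolled subjects, and Section 11.2.3 promises event reporting for all subjects. The analysis-set definitions in Section 11.2.1 are not limited to three cohorts. Only the baseline list in Section 11.1.2 omits the cohort by name. That is missing detail, and Section 11 refers to a study-specific statistical analysis plan that may supply it.

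A reader might also fear that these subjects could enter the primary analysis. The restriction of the primary test to the Main Cohort already prevents that.

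**Conclusion.** The point holds as a statement about the enrollment ceiling. As written, the maximum of 926 can be exceeded by following the protocol, because the conditional CT Imaging Cohort was left out in both places where the total appears. The correct maximum is 926 + (200 − m), from 926 to 1,126.

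It is tempting to say that the maximum simply is 1,126, or 22% too low as stated. That figure is an outer bound. It requires that no Main Cohort subject joins a substudy designed to recruit from that cohort. The intermediate values rest on assumed values of m, since the protocol gives no expected uptake.

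The conclusion assumes that the separate cohort really is additional to the 696, which follows from its description and from when it opens. The study design figures are not reproduced in the text reviewed, so whether they show the cohort could not be checked. The primary hypothesis, sample size and power do not change.

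**What to change.** 1. In the Synopsis (planned number of subjects) and in Section 7.3, restate the total along these lines: up to 926, plus any CT Imaging Substudy shortfall enrolled in a separate CT Imaging Cohort (0 to 200; absolute maximum 1,126).
2. Add a CT Imaging Cohort row, 0 to 200, to the cohort table in the Synopsis, and list the cohort among those itemized in Section 7.3.
3. For consistency, name the cohort in Section 11.1.2 so that its baseline data have a stated place.

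No change is needed to Section 11.1.1 or to the substudy analysis in Section 11.1.4.

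The cost is protocol wording and a larger published ceiling. Under Section 16.3 an amendment goes to the ethics committees for review, so the change is best bundled with the next revision and made before any separate CT Imaging Cohort opens.
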